1.3. Duration

3 years.

1.4. Keywords

von Willebrand disease, von Willebrand factor, diagnosis, genetic testing, diagnostic platform, registry database, LOPD, NGS, custom panel, Data encryption and security, Cloud computing, Software usability, API, IaaS, e-Learning, BPM, Translational research, Software usability, Software scalability, Data modeling, Iterative and Incremental Development, e-Training, Web 2.0, Machine Learning.

1.5. Correspondence to

[name] [name]

Chairman Servicio de Hematología.
Complexo Hospitalario Universitario A Coruña (Edificio Materno Infantil)
Servicio de Hematología y Hemoterapia
[name]
E mail: [contact]

2. Summary of grant request

The present Project is a third phase of the previous **PCM-EVW-ES** Project (*Batlle et al. Thromb & Haemost 2015*) with the aim of its extension, further analysis with an innovation development in the field of VWD based in the newer recently available methodologies. The aim of this project is to help the physician in a **more uniform characterization and therapy of VWD** in clinical practice, at an international level. **A reduction of the expenses in the diagnosis process** by using the new methodologies is pursued.

The **specific objectives** and corresponding **tasks** of the present project are as follows:

Main objective is:

1. Extension of the central phenotypic and NGS genotypic characterization of the VWD in Spain, through the prospective recruitment in the Spanish VWD cohort of approximately 500 new patients with local historical VWD diagnosis (from approximately 38 centres).

Secondary objective is:

1. Development of an electronic platform using this proposed algorithm. In a second step, some other mutation-oriented tests or investigations could be carried out for confirmation.

This project involves leading innovation and translational research with a direct impact on the quality of clinical care (applicability). To our knowledge there is no similar project in this field. Potential patents may derive from this project. It involves also development of e-learning and new information technologies (debate forum, ads, google search engine). This project may promote international collaboration. Development of an algorithmic platform that facilitates diagnosis and therapy orientation of VWD in clinical practice using the selected data from the overwhelming amount of information that new technologies, such as NGS, are producing.

3. State of art/study background

VWD overview in Spain

A previous published multicenter study on the situation of VWD in Spain showed a frequency of this disease and distribution of the different types similar to that observed in some other European countries. The results of a concise survey on the diagnosis of VWD showed a frequency fivefold greater in Spain than that expected from epidemiological studies in other European countries; this may result from overdiagnosis and/or a higher prevalence of VWD. These results clearly reinforce the need for the Spanish VWD registry. The rate of response to our questionnaire was 66.6% (36 centers, including the 5 Hemophilia Treating Centers), which is very similar to the mean responses indicated in the study of Rodeghiero et al (65%) [30]. From an epidemiological point of view, the entire population analyzed, corresponding to the responding centers, was 22.8 million inhabitants; this represents 49% of the global Spain population. When also taking the wide geographic distribution of the participating centers into account, we believe it is possible to extrapolate our findings to the entire country.

It is particularly noteworthy that in classified patients the distribution of VWD types is quite similar to that observed by Rodeghiero et al [30], especially for types 1 and 2.

Globally, participant investigators experienced difficulty in characterizing about a third of the patients with a definite diagnosis of VWD.

Diagnostic strategy

The data obtained in that survey for diagnostic parameters indicated that the more widely used tests are FVIII activity (FVIII:C), VWF:RCo, and VWF:Ag, and, to a lesser extent, VWF:CB. The RIPA at low ristocetin concentration (that allow identified the type 2B), the plasma VWF capacity to bind exogenous FVIII (VWF:FVIIIB) (that can distinguish between hemophilia and type 2N VWD) and the multimeric analysis were test very little used due to their complexity. The limited use of these methods may lead to underdiagnosis of some patients. Also, the complexity, high cost, and experience required to perform a molecular study constitute the main reasons for that only five centers carried out this study by Sanger and the 50% of participants never request this study its low use. One of the conclusions of this the Spanish study was that because of the complexity and/or difficulty in performing some of the tests used in the diagnosis of VWD, supporting the centralization of these tests in laboratories that have the experience necessary to achieve a more uniform characterization.

The Molecular and Clinical Profile of von Willebrand Disease in Spain (PCM-EVW-ES) Project. Spanish Registry

Motivated by the success and experience of the European Project MCMDM-1VWD, a Spanish Registry on VWD has been initiated. Several European countries already have their own registry. In order to achieve a better comprehension of this complex pathology, it is necessary to rely on a patient database that must be as much extensive and detailed as possible [31].

A main feature of the PCM-EVW-ES is that the analysis of the samples has been centralized in three laboratories that have the experience necessary to achieve a more uniform characterization. It should be emphasized that this study was not intended as a prevalence study or as a quality assessment of the participant laboratories. The main goals of the study are:

- i. An assessment of the real diagnosis and therapeutic situation of VWD in Spain in normal clinical practice;
- ii. The achievement of a platform of recruited patients with the best possible characterization;
- iii. The development of a Spanish Working Group on VWD (recently created);
- iv. Participation in international projects on VWD (European Union VWD Group, Zimmerman Project, Type 3 VWD International "Registry Inhibitor Prospective Study (3WINTERS-IPS)";
- v. Elaboration of practical guidelines on diagnosis and therapy of VWD in Spain.

There are several additional aims to the study, summarized as follows:

- 1. To ascertain the clinical profile of those patients diagnosed with VWD who had been referred to the Spanish centers and were in active follow-up in 2011. The bleeding score is used to establish the bleeding history.
- 2. To characterize the diagnosis of types and subtypes up to the most complete hierarchical level, based on the revised and updated classification of the ISTH-SSC VWF.
- 3. To know the modality of therapy used.
- 4. To register and analyze any genetic abnormality.
- 5. To register patients with bloodborne diseases, such as human immunodeficiency virus, hepatitis B, and hepatitis C infected patients, and under retroviral therapy.
- 6. To develop knowledge on alloantibodies against VWF and to evaluate any corresponding treatments.
- 7. To record the history of major surgeries and types of treatment.

Study Cohort

Patients of any age previously diagnosed locally with VWD or referred from any hospital department or from family care that fulfill one or more of the following inclusion criteria: 1) VWF:Ag, VWF:RCo and/or VWF:CB ≤30 UI/dL (%), observed on two or more occasions; 2)detection of multimeric abnormalities; 3) in case of isolated FVIII deficiency it will be necessary to provide demonstration of a decreased VWF:FVIIIB; 4) presence of VWF mutations; 5) presence of RIPA at a low ristocetin concentration.

Exclusion criteria: Presence of any data suggesting acquired Von Willebrand syndrome. The definitive diagnosis will be performed centrally.

Genetic analysis: Initially it was planned to analyze by using the expensive Sanger method either some exons or the whole *VWF* in some patients with types 2 and 3 VWD. However, thanks to the availability of the new methodology based on NGS, much less expensive, the genetic analysis was extended to all the recruited patients.

3.1. Previous results from the PCM-EVW-ES Project.

A cohort of 556 patients from 330 families previously diagnosed as VWD at the local centres were analyzed centrally. VWD was confirmed in 480 [31]. NGS of the whole coding *VWF* was carried out in all recruited patients, compared with the phenotype, and a final diagnosis was established. A total of 238 different VWF mutations were found, 154 were not included in the Leiden Open Variation Database (LOVD). Of these patients, 463 were found to have *VWF* mutation/s. A good phenotypic/genotypic association was estimated in 96.5% of the patients. One hundred and seventy-four patients had two or more mutations. Occasionally a predominant phenotype masked the presence of a second abnormality. One hundred and sixteen patients presented with mutations that had previously been associated with increased VWF clearance. RIPA unavailability, central phenotypic results disagreement and difficult distinction between severe type 1 and type 3 VWD prevented a clear diagnosis in 70 patients. The NGS study facilitated an appropriate classification in 63 of them. The remaining seven patients presented a *VWF* novel mutation pending further investigation. In five patients with a type 3 and two with a type 2A or 2B phenotype with no mutation, an acquired von Willebrand syndrome (AVWS) was suspected/confirmed.

A 42.3% local/central phenotypic diagnosis discrepancy was observed indicating the practical difficulties/drawbacks of VWD diagnosis. A 96.5% phenotypic/NGS genotypic association was observed, suggesting the possibility of incorporating the NGS in the initial VWD work-up. Comparative analysis of sensitivity and specificity with traditional gold standard sequencing method showed values of nearly 99% and 98% respectively.

These data seem to support the NGS as a first line efficient and faster paradigm in VWD diagnosis. Anew algorithm for the initial study of VWD was proposed. It includes family history, bleeding score, VWF:Ag, VWF:RCo/VWF:GPIb α assay, platelet count and peripheral blood smear, and VWF molecular study by NGS, using a cut-off for VWF:Ag of \leq 30 IU/dL in type 1 VWD, considering all of them as essential information to predict and manage the severity of the clinical bleeding phenotype. In a second step, some other mutation-oriented tests or investigations could be carried out for confirmation.

Thus, this does not intend at all to transmit the message of molecular analysis as a surrogate approach of a phenotypic study. We are now developing an algorithm platform as a software based on these parameters that will help in the diagnostic process in the clinical setting. It includes a *VWF* mutations database that will be updated regularly, taking into account the *VWF* sequence variants that are known not to influence VWF levels or cause a clinical disease.

Recently a similar study in a Portuguese cohort has been published [32] confirming the NGS value in VWD diagnosis.

4. Hypothesis

- i. Homogeneous characterization of patients with VWD is not generally accomplished in Spain and also in many countries. There is considerable confusion between variant and non-variants forms. The methods, which would allow us a better characterization of the patients, are not available in all centers due to the fact that they lack the necessary infrastructure to carry them out.
- ii. The possibility to enlarge the number of patients by the reopening of the project will allow the validation of the proposed algorithm (phenotype study and NGS of the *VWF* as a first line diagnostic approach) enriching our knowledge of VWD spectrum in our population.
- iii. The feasibility to develop linkage analysis and expression studies of certain mutations can help to establish their possible common origin and explain how the mutation affect the protein synthesis or secretion deeping in the molecular basis of VWD at the population or individual level
- iv. Currently the new diagnostic methodologies are very helpful but generating overwhelming amount of information impossible to manage at clinical setting. The creation of an algorithmic platform with a regularly updated database that includes processed information in regard to mutations and approved international criteria, to guide the physician in the VWD diagnostic process and recommended therapy should be extremely helpful in facilitating a more uniform characterization and therapy of VWD patients in clinical practice at an international level. Also another main point might be a reduction of the cost (work effort and expenses) in the diagnosis process by using the new methodologies as it is the NGS.

5. Specific objectives description, rationale, methodology and corresponding tasks

The present project was already approved by the Galicia Ethical Committee (CEIC) (Annex I).

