5.1. Specific main objective

Extension of the central phenotypic and NGS genotypic characterization of the VWD in Spain, through the prospective recruitment in the Spanish VWD cohort of approximately 500 new patients with local historical VWD diagnosis (from approximately 38 centres)

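### If the listed entry criteria govern the extension, the cohort is selected at a VWF level of 30 and cannot validate the algorithm's VWF:Ag ≤30 cut-off for type 1

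*Protocol*

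**What the plan says.** The Study Cohort text in section 3 takes patients with a local VWD diagnosis, or referred from elsewhere, "that fulfill one or more of the following inclusion criteria". The five criteria are:

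1. "VWF:Ag, VWF:RCo and/or VWF:CB ≤30 UI/dL (%), observed on two or more occasions"
2. an abnormal multimer pattern
3. "in case of isolated FVIII deficiency it will be necessary to provide demonstration of a decreased VWF:FVIIIB"
4. a known VWF mutation
5. a RIPA response at low ristocetin concentration

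Section 3.1 describes the proposed first-line algorithm. It combines history, bleeding score, VWF:Ag, an activity assay, platelet count and smear, and VWF sequencing by NGS, with a VWF:Ag limit of 30 or below "IU/dL in type 1 VWD, considering all of them as essential information to predict and manage the severity of the clinical bleeding phenotype".

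Section 4, hypothesis ii, says that reopening the project "will allow the validation of the proposed algorithm". A parenthesis there describes the algorithm as phenotyping together with NGS at first line.

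Section 5.1 describes the new patients only as "approximately 500 new patients with local historical VWD diagnosis". It gives no laboratory criteria, and the protocol has no other eligibility list.

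**The concern.** To judge a threshold, one needs patients on both sides of it who entered by the same rule. Here the level-based entry rule and the algorithm's type 1 cut-off share the value 30. Patients above it on every assay come in only because an abnormality has already been shown. Such a sample says little about how many true type 1 patients the cut-off misses. A comparison of sequencing yield above and below 30 would partly reflect how patients got in.

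This matters because the algorithm is to be turned into an electronic platform (section 5.2). Section 7, item III, expects that platform to be validated and accepted internationally, and section 13.1 lists platform validation as a staff task. A cut-off that looks confirmed because it was also the entry condition would pass into that tool. Selection at entry cannot be undone in the analysis.

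**Working it through.** The protocol gives no sensitivity, specificity or yield for the cut-off, so there is no figure to reproduce. The check is mainly one of logic.

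**Routes into the cohort.** Take a locally diagnosed patient with VWF:Ag, VWF:RCo and VWF:CB all between 35 and 45, and a type 1 pattern.
- Criterion 1 is closed, because no assay is at or below 30.
- Criterion 2 is closed, because multimers are normal.
- Criterion 3 is closed, because there is no isolated FVIII deficiency.
- Criterion 5 is closed, because there is no low-dose RIPA response.
- Criterion 4 is open only if a VWF mutation is already known.

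Now take a patient with VWF:Ag of 40 and VWF:RCo of 25 on two occasions. Criterion 1 is met through VWF:RCo, and no mutation is needed. So patients above the algorithm's VWF:Ag limit can be present, but they were selected on low activity.

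**Yield among mutation-only entrants.** Section 3.1 reports NGS sensitivity of nearly 99% against traditional sequencing. A patient admitted on a known mutation will therefore almost always be NGS-positive, whatever the yield in comparable unselected patients.

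**Direction of the bias in sensitivity.** Let S be the true sensitivity of VWF:Ag ≤30 for type 1. Let a be the rate at which type 1 patients above 30 gain entry, relative to those at or below 30. Then

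apparent sensitivity = S / (S + (1 − S)·a)

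Neither S nor a is in the document, so the values below are assumptions.

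| S | a = 0 | a = 0.10 | a = 0.25 | a = 0.50 | a = 1 |
|---|---|---|---|---|---|
| 0.40 | 1.00 | 0.87 | 0.73 | 0.57 | 0.40 |
| 0.60 | 1.00 | 0.94 | 0.86 | 0.75 | 0.60 |
| 0.80 | 1.00 | 0.98 | 0.94 | 0.89 | 0.80 |

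For example, with S = 0.60 and a = 0.25: 0.60 / (0.60 + 0.40 × 0.25) = 0.60 / 0.70 = 0.86. The estimate is right only at a = 1. Because of the low-activity route, a need not be 0.

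**Spread from central assessment.** Section 3.1 reports 480 of 556 patients confirmed centrally: 480/556 = 86.3%, leaving 76 (13.7%) unconfirmed. At that rate about 500 × 76/556 = 68 of 500 new patients would be unconfirmed. They would give some spread, but they come from the same locally selected pool and are not a separate reference group.

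**The case against.** Four objections deserve weight.

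*The protocol does not claim to validate the cut-off.* Hypothesis ii does not name it, and its parenthesis stresses phenotype plus NGS. No stated objective estimates the performance of ≤30. This stands in part. The point is confined to the cut-off, and agreement between phenotype and NGS within the cohort can still be described. But section 3.1 makes the cut-off part of the algorithm, and hypothesis ii claims validation of that algorithm without excepting it.

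*The list belongs to the existing registry.* It sits in the background section, and section 5.1 asks only for a local diagnosis. This is a real condition on the finding. Against it, the project is called a third phase and a reopening, and no other list is given. If section 5.1 alone governs, the truncation at 30 falls away, though there is still no non-VWD reference group.

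*The gate and the cut-off are not the same.* The algorithm uses VWF:Ag alone, while criterion 1 also accepts low VWF:RCo or VWF:CB. Central retesting can also place entrants above 30. This stands. A reader might infer that the upper side is empty, or that everyone above the cut-off is mutation-positive by selection. The criteria do not support that. It holds only for a type 1 pattern with all three local assays above 30.

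*Criterion 4 entrants may be few.* The Diagnostic strategy text in section 3 reports that only five centres did molecular study and half of the participants never requested it. That limits distortion of the overall yield. It also means that patients above 30 on every assay would seldom have a way in. The same text says RIPA, VWF:FVIIIB and multimers were little used, so criterion 1 is likely to be the main gate in practice.

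**Conclusion.** The point holds with a limited scope. If the section 3 list governs the extension, the cohort cannot validate the VWF:Ag ≤30 type 1 cut-off. Locally diagnosed patients above 30 on all three assays with no listed abnormality have no route in, and those with a type 1 pattern enter only on a known mutation. NGS yield in patients admitted only on a mutation is close to 100% by construction.

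Selective entry of this kind raises apparent sensitivity whenever type 1 patients above 30 enter less readily than those below. The amount cannot be computed, because the document gives no counts by entry criterion. It is tempting to assume a true yield above 30 of, say, 40% to 70% and call the shortfall from 100% a bias of 30 to 60 percentage points. That range only restates the assumption and has no source in the protocol.

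The main objective, central phenotypic and genotypic characterization, is not affected.

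**What to change.** - Reconcile the Study Cohort list in section 3 with section 5.1, and state which governs entry to the extension.
- If the ≤30 gate stays, limit hypothesis ii to agreement between phenotype and NGS within the selected cohort, and state that the ≤30 cut-off is adopted and not validated.
- Record for each patient every entry criterion met.
- Report NGS yield and central confirmation by VWF:Ag band (30 or below, above 30) without patients who qualified only by criterion 4. Show those patients separately, and label the comparison as descriptive, since the upper band is still a selected group.
- Keep a one-line log of local levels for locally diagnosed patients who are turned away.

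The cost is some wording, one extra field per patient, a small screening log and a narrower validation claim. Dropping the gate is not needed for this. It would change the registry's case definition, reduce comparability with the first 556 patients, and still supply no non-VWD reference group.

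### Hypothesis ii promises validation as a first-line diagnostic approach, but a cohort of previously diagnosed patients supports only concordance and type classification

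*Protocol*

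**What the plan says.** Section 4, hypothesis ii: "The possibility to enlarge the number of patients by the reopening of the project will allow the validation of the proposed algorithm", the algorithm being phenotype study and NGS "as a first line diagnostic approach". Section 3.1 gives its intended use: an "algorithm for the initial study of VWD was proposed". Section 7 III expects a validated platform usable in clinical practice, and section 13.1 lists platform validation among the funded tasks.

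The main objective (sections 2 and 5.1) is to recruit "approximately 500 new patients with local historical VWD diagnosis". The Study Cohort text in section 3, which describes the registry, takes patients with a previous local diagnosis or a referral. Each must meet at least one of five criteria, all of them abnormal VWF findings. A VWF mutation alone is enough.

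Section 3.1 reports the earlier phase: 556 locally diagnosed patients from 330 families, of whom "VWD was confirmed in 480", with mutations in 463 and a phenotype/genotype association of 96.5%. NGS was "compared with the phenotype, and a final diagnosis was established". Of 70 patients without a clear diagnosis, "The NGS study facilitated an appropriate classification in 63 of them".

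None of the five limitations in section 6 mentions selection on a prior diagnosis.

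**The concern.** A first-line approach is applied to people not yet diagnosed, many of whom may turn out not to have the disease. Its accuracy depends on how it performs in that mix. Patients who already carry a local diagnosis are past that stage, and no analysis plan can supply patients who are not enrolled.

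Concordance among previously diagnosed patients could then be reported, and built into a platform meant for international use, as if it were accuracy at first work-up. Section 3.1 already moves from the 96.5% association to suggesting NGS in the initial work-up.

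A second, smaller matter is the reference. In the earlier phase the final diagnosis was settled after NGS had been compared with phenotype. Agreement of NGS with a diagnosis set that way is partly built in.

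**Working it through.** **1. The protocol's own figures (section 3.1).**
- Association: 463/480 = 96.5%, which matches the reported value; 463/556 = 83.3% does not. The figure therefore appears to be a share of confirmed patients, although its derivation is not stated. Read that way, it says nothing about specificity.
- Sensitivity and specificity: "Comparative analysis of sensitivity and specificity with traditional gold standard sequencing method showed values of nearly 99% and 98% respectively". The comparator is another sequencing method, so this is analytical accuracy, not accuracy for disease.

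**2. Who is in the cohort.**
- Extension (sections 2 and 5.1): patients with a previous local diagnosis.
- Registry criteria (section 3, Study Cohort): referred patients too, but with an abnormal VWF finding required. One qualifying finding is a mutation, which is the kind of result NGS itself produces.
- No group of unselected suspects is described in either place.

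**3. What the unconfirmed patients could give.**
- Unconfirmed in the earlier phase: 556 − 480 = 76; 76/556 = 13.7% (exact 95% CI 10.9% to 16.8%).
- At the same rate (assumption): 500 × 0.1367 = 68.3, with 54.6 to 84.0 over that interval. For the 400 patients budgeted in section 13.2: 400 × 0.1367 = 54.7.
- Precision of a specificity from such numbers, with illustrative results: 61/68 = 90% has an exact 95% CI of 80% to 96%; 50/55 = 91% has 80% to 97%.
- These intervals treat patients as independent. With 556 patients in 330 families they are probably too narrow.

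**4. Why predictive values do not carry over.** The protocol gives no clinical sensitivity or specificity and no first work-up prevalence, so all three are assumed: sensitivity (Se) 96.5%, specificity (Sp) 90%, and several prevalences (p).

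PPV = Se × p / [Se × p + (1 − Sp)(1 − p)]

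| Prevalence | PPV |
|---|---|
| 86.3% (480/556, earlier phase) | 98.4% |
| 50% | 90.6% |
| 30% | 80.5% |
| 10% | 51.7% |

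At 10% prevalence, PPV runs from 34.9% (specificity 80%) to 84.3% (specificity 98%). NPV moves the other way: 80.3% at 86.3% prevalence and 99.6% at 10%, with specificity 90%.

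**5. Role of NGS in the earlier reference.** 63/70 = 90% of the unclear patients were classified with its help. The denominator behind the 70 is not stated: 70/556 = 12.6% and 70/480 = 14.6%. For 500 recruits that would be about 63 or 73 without a clear type from phenotype alone, if the rate recurred.

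**The case against.** The strongest reply is that validation is one undefined word in a hypothesis. The listed objectives are characterisation and a platform, and clinical specificity and predictive value are nowhere named as endpoints. Hypothesis i is about confusion between variant forms, so validation could mean correct typing within VWD, for which this cohort is suitable. This stands in part: the listed objectives are unaffected, and a reader should not infer that the protocol promises a specificity. But hypothesis ii says first-line and section 3.1 says initial study. If typing is what is meant, the text should say so.

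Four stronger readings are tempting and are not supported:
- *That no specificity could be computed.* Unconfirmed recruits would allow one, but only among people already labelled with VWD.
- *That all 76 unconfirmed patients were local misdiagnoses.* Section 3.1 does not explain them, nor say whether the seven with suspected or confirmed acquired von Willebrand syndrome are among them.
- *That no patient at first work-up can enter.* The Study Cohort text admits referrals. They are selected on an abnormal finding, which is a different point.
- *That the extension's reference is circular.* This is documented only for the earlier phase. The extension's reference and reading order are not stated and may be in a statistical analysis plan that is not shown. Section 13.2 has samples go to La Coruña first and aliquots then go to Barcelona for sequencing. That separates the work but does not establish blinding.

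It is also fair to say that comparing NGS with central phenotype sets one component of the algorithm against another. That comparison is concordance, not independent validation.

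**Conclusion.** The point holds in limited form and should be corrected. The planned recruitment supports statements on phenotype/genotype concordance and on the contribution of NGS to typing in patients with a prior local diagnosis. It does not support diagnostic accuracy at first work-up, which is what hypothesis ii claims and what section 7 III can be read to claim.

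This conclusion rests on the stated recruitment and entry criteria, not on a projection. The sizes do rest on assumptions. About 68 unconfirmed patients in 500 (or about 55 in 400) presumes that the earlier 13.7% recurs, and the resulting intervals ignore family clustering. The predictive values are illustrations with assumed inputs.

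The dependence of the reference on NGS is established for the earlier phase only. For the extension it justifies a reporting safeguard and no more.

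**What to change.** - **Section 4, ii:** restate as describing phenotype/genotype concordance, and the contribution of NGS to type classification, in patients with a prior local VWD diagnosis.
- **Section 7 III:** limit validated to the same scope.
- **Section 6:** add that patients are selected on a prior diagnosis (or, if referred, on an abnormal VWF finding), so no conclusion on accuracy at first work-up will be drawn.
- **Reporting:** give any agreement of NGS with type against the central phenotypic diagnosis recorded before NGS results are used. Count patients without a clear pre-NGS type as unclassified, and report separately how many NGS resolved. Call the result concordance between two components of the algorithm.

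This costs wording in three sections and the recording of one diagnosis before NGS is used, with no extra patients or assays. The downside is a narrower claim. A first-line claim would need a separate study in patients at first work-up.

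### Hypothesis ii promises validation of an algorithm that contains NGS, but the protocol names no reference diagnosis independent of NGS and does not require the phenotypic class to be fixed before NGS is known

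*Protocol*

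**What the plan says.** - **Claim.** Section 4, hypothesis ii: "the reopening of the project will allow the validation of the proposed algorithm". The algorithm is defined there as phenotypic work plus VWF sequencing by NGS, used first line. Section 7 (item III) expects a validated platform, and Section 13.1 lists platform validation as a staff task without a method.
- **Earlier workflow.** Section 3.1: NGS was run in every recruited patient, "compared with the phenotype, and a final diagnosis was established". Missing RIPA, disagreement between central phenotypic results, and the difficulty of separating severe type 1 from type 3 "prevented a clear diagnosis in 70 patients". Then: "The NGS study facilitated an appropriate classification in 63 of them".
- **Extension.** The main objective (Section 5.1) extends the same central phenotypic and NGS work to about 500 new patients. The Study Cohort text in Section 3 places the definitive diagnosis at the central level without saying which data may inform it. It also lists a known VWF mutation as inclusion criterion 4.
- **Sample flow.** Section 13.2: samples reach A Coruña first, and aliquots then go to Barcelona for molecular analysis.

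**The concern.** A diagnostic algorithm is validated by comparing its output with a diagnosis reached without it. Here NGS is a component of the algorithm and, in the only workflow described, also an input to the final diagnosis. Comparing the two is partly comparing NGS with itself, which tends to overstate agreement.

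The weaker comparison, NGS against the phenotypic class, is sound only if that class was settled before anyone who assigns it knew the genotype. The protocol does not require this.

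The word validation is therefore at stake. The extension could report high agreement that the design cannot interpret. The order of recording operates when samples are read, so it belongs in the protocol and should not wait for an analysis plan.

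**Working it through.** **Step 1. Inputs (all from Section 3.1).** Recruited: 556 patients from 330 families. No clear diagnosis: 70. Classified with the help of NGS: 63.

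**Step 2. How far NGS entered the final diagnosis.**

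- Unclear patients resolved with NGS: 63/70 = 90.0%. The Wilson 95% interval is 80.8% to 95.1%, ignoring clustering in families.
- Share of all recruited: 63/556 = 11.3%.
- If the same rate held in the extension (an assumption): 500 × 63/556 ≈ 57 patients, or 400 × 63/556 ≈ 45 on the 400 budgeted in Section 13.2.

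These figures show that NGS informed the final diagnosis. They do not measure bias. The text does not say how the 63 were treated in any agreement figure, or whether NGS also influenced the final diagnosis of patients outside the 70.

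**Step 3. Which comparison could carry the claim.**

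| Comparison | Independent of NGS as described? | What it could show |
|---|---|---|
| NGS against traditional sequencing (nearly 99% and 98%, Section 3.1) | Yes, for the sequence | Analytic accuracy of sequencing, not correct VWD classification |
| NGS against central phenotypic class | Only if the class is fixed before NGS is known; not required anywhere | Agreement between two components of the algorithm |
| NGS, or the algorithm, against final diagnosis | No; the final diagnosis follows the NGS comparison | Circular |
| Algorithm against a diagnosis made without NGS | No such diagnosis is named | Validation |

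**Step 4. Does other text supply the missing reference?**

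- The second-step tests (Sections 3.1 and 5.2) are optional and mutation-oriented, so they are chosen in the light of the genotype.
- The linkage and expression studies (hypothesis iii) concern certain mutations and are stated as a possibility.
- Section 13.2 separates the laboratories and puts A Coruña first, but this is logistics: no phenotypic class is locked and no result is withheld.
- Section 13.1 gives one half-time investigator the central phenotypic analysis, the mutation database, the controversial cases and platform validation. No separation of readers is described.

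None of these is a reference diagnosis independent of NGS.

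**The case against.** The strongest reply is that Section 3.1 reports an association between phenotype and NGS, made before the final diagnosis was set, and not an agreement between NGS and that diagnosis. The same section gives a 42.3% discrepancy between local and central phenotypic diagnoses and counts 70 patients as unclear for largely phenotypic reasons. Both suggest that a central phenotypic class existed separately from NGS.

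This stands. It rules out a stronger reading that a reader might infer, namely that NGS shaped the phenotypic class and inflated the earlier result: "A good phenotypic/genotypic association was estimated in 96.5% of the patients". The 63 patients show that NGS informed the final diagnosis, and no more. No counts or criterion are given for the 96.5%, so its basis cannot be rebuilt from the protocol.

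It is also fair that validation is not one of the two formal objectives, that the protocol does not say outright that the earlier workflow will be repeated, and that the Study Cohort text describes the earlier project. Section 3.1 suggests only that NGS might be added to the initial work-up, and Section 4 follows text saying that molecular analysis is not a surrogate for phenotypic study. Masked reclassification from stored laboratory results would remain possible later, at the price of a second reading.

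These points limit the finding without removing it. The validation claim is explicit, the extension is described as more of the same work, and nothing replaces the earlier workflow or secures the order of recording.

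**Conclusion.** The concern holds as a gap between a stated claim and the design. As written, the extension can describe phenotype and genotype and report how often they agree, but it cannot validate an algorithm that contains NGS. It is worth fixing before new samples are read.

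The size of any incorporation bias cannot be derived. What is known is that NGS assisted the final classification in 63 of 556 earlier patients (11.3%).

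The conclusion rests on two assumptions: that the extension follows the earlier workflow, which its description as an extension supports but does not state, and that the annexes, which are not at hand, set no reference diagnosis or masking rule.

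It should not be read as a finding that the 96.5% is wrong or biased, because the documents do not allow that to be judged either way.

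**What to change.** 1. Have A Coruña record and lock a phenotype-only class for each patient, with unclassifiable as an allowed value, before Barcelona's NGS result is released. The sample flow in Section 13.2 already runs in this order.
2. Report agreement of NGS with the locked class and, separately, the share of unclassifiable patients whom NGS resolves.
3. In both, show apart the patients who entered on a known VWF mutation (inclusion criterion 4, if it applies to the extension). Withholding the Barcelona result cannot mask a mutation known at entry.
4. Reword hypothesis ii to claim agreement between phenotype and NGS. Keep the claim of validating the combined algorithm only if a reference diagnosis independent of NGS is named.

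The cost is protocol wording, one locked database field and a release rule; no new test is needed. The drawbacks are some sequencing of work between the laboratories and an agreement figure that may fall below 96.5%.
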